Training of clinics. At delivery of the Balance+Weight device to the clinic, a one-hour in-service will be performed by study personnel to train all providers and medical assistants on its proper use and the entry of data into the electronic medical record. This training will include how to operate the device and how to use the accompanying documentation with the reported data to inform clinical decision-making. This documentation will include threshold values for likelihood of the patient's balance being Within Normal Limits as well as the change in value that would indicate a change in the patient's balance status along with appendices that contain the published peer-reviewed journal articles upon which these recommendations are based. Upon request by the clinic, study personnel will repeat the training if refreshers are needed by clinic staff. An unlimited number of refresher trainings are permitted for each clinic, and the number of trainings requested per clinic will be recorded.

Incorporation of quantitative postural control assessment device into clinic flow including immediate feedback on clinical utility. Each participating clinic will place the study device in a location to allow its use instead of their weight scale. In the Balance+Weight arm, the device is capable of either just giving weight, or of providing balance data if the patient stands quietly with eyes closed for 30s. In the Weight Only arm, the device only gives a weight measurement, just as a standard weight scale would. In both

cases, the provider and their staff make their own clinical decisions as to which patients to make measurements of and how to use the provided information. The medical assistant may choose to enter the appropriate values into the medical record and continue with any other standard procedures in that clinic setting as part of the rooming or initial evaluation process. The provider can then examine the recorded balance measurement along with their standard examination and determine whether any further evaluations in that clinic or referral to a specialist, physical therapy, or other falls prevention is appropriate and record that diagnosis or referral into the medical record.

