Immediate feedback from provider on clinical decision-making process. After each patient encounter in which the provider assessed balance using the Balance+Weight device, the provider who made a clinical decision regarding balance or falls risk is asked to press a button on a small kiosk that we will provide which logs their agreement with the statement, "The balance measurement influenced my clinical decision making with this patient." These kiosks from Happy-Or-Not.com are completely wireless and use their own 3G network to communicate the results of a single 4-point Likert scale question back to a central server that the study staff can monitor to collect data and get a real-time indication of whether the providers are using the Balance+Weight device.

Crossover of sites after 9 months. At the 9-month point, study personnel will go to every site to reprogram each device from Balance+Weight mode to Weight Only mode or vice versa, and to move the immediate feedback kiosks to the new Balance+Weight sites.

Data pull of clinic-level diagnosis and referral data. At or just after the crossover between sites has occurred, study personnel in conjunction with the IT departments at participating sites will pull the clinic diagnosis and referral data for all participating providers. After Casey et al.[15], our initial plan is to count instances of the following Common Procedural Terminology Category II codes:

- (Primary) CPT II 3288: Assessment of falls risk
- CPT II 0518: Development of a falls care plan
- CPT II 1101: Documentation of falls in past year (no falls/ single fall without injury)
- CPT II 1100: Documentation of an injurious fall/ multiple falls
- Other referral codes as appropriate

Because CPT codes are updated each calendar year, we will review the new codes each year and revise this code list as new codes related to falls assessment are added or subtracted. We will pull this data from both the 9 months of participation in the study, as well as the same 9 month period in the calendar year before the study began as a historical control. The data will be pulled again upon completion of the study for the second 9-month period.

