Statistical analysis of clinical billing data. Counts of each code listed above will be tabulated for each provider during the 9 month period in the year before beginning the trial, during the 9 months with the Balance+Weight device, and during the 9 months with the Weight Only device; normalized by the total patient encounters by that provider over the same time periods to get incidence rates of each code for each condition (historical, Balance+Weight, Weight Only). The incidence rate ratios of Balance+Weight to the other two conditions will then be calculated, and the 95% confidence intervals of those incidence rate ratios will be calculated to see which are significantly different from 1.0, as we have previously done with other epidemiological data [16]. Each code is considered separately, because it is possible that multiple codes may be used in a single encounter, but as the primary goal of a quantitative postural control assessment is to trigger further action by the provider to confirm that the individual has a balance impairment, the primary variable of interest is CPT II 3288: Assessment of falls risk. This approach would statistically test the hypothesis that the provider is more likely to proceed in any falls risk algorithm such as STEADI on to a further assessment of falls risk with quantitative postural control information in addition to patient self-report or clinical observation. Using the data reported by Casey et al. in their implementation of STEADI [15], where they reported an initial rate of an assessment of falls risk of 19% across 16 providers over 3 months leading to 360 screens, we estimate that with 10 providers in each group over 9 months there could be approximately 3552 patient encounters in each group, or 7105 patient encounters over 18 months. With this number of patient encounters, we would have sufficient power to detect an incidence rate ratio of 1.1, or a 10% increase in Assessments of falls risk. Given the reported rate from Casey et al. that 35% of assessed patients score as high risk, that 10% increase could lead to approximately 47 additional high-risk individuals being identified, which we deem a clinically significant improvement.

IV. List of References

1. World Health Organization. WHO Global Report on Falls Prevention in Older Age.; 2007. doi:978 92 4 156353 6.

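### The Balance+Weight to historical ratio is tested on the same footing as the randomised contrast, with no Weight Only to historical interval and no baseline adjustment to separate a device effect from drift

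*Combined protocol and SAP*

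**What the plan says.** Section III.6 (statistical analysis of clinical billing data) tabulates each code per provider, divided by encounters, for the historical, Balance+Weight and Weight Only conditions. The plan names only two comparisons: "The incidence rate ratios of Balance+Weight to the other two conditions will then be calculated". Both ratios then face one and the same significance rule, which section III.6 words as follows: "the 95% confidence intervals of those incidence rate ratios will be calculated to see which are significantly different from 1.0". Among the codes, "the primary variable of interest is CPT II 3288: Assessment of falls risk". The section does not say which of the two ratios carries the conclusion. It describes no Weight Only to historical ratio, no period term and no baseline-adjusted comparison.

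Section III.4 (data pull) collects the nine study months "as well as the same 9 month period in the calendar year before the study began as a historical control". Section III.3 describes the same window. Section III.4 (incorporation into clinic flow) says that in the Weight Only arm "the device only gives a weight measurement, just as a standard weight scale would".

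Sections III.1 and III.4 (randomization of clinics) set up a randomised two-period crossover of nine plus nine months, in which each clinic is also its own control.

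**The concern.** Balance+Weight to historical is a before-and-after comparison. Any change in coding habits since the historical window, and any effect of taking part in a falls study, goes into it together with the device. Section III.4 itself expects the relevant code list to change from one calendar year to the next. Yet the stated rule, an interval that excludes 1.0, is the same for this ratio as for the randomised one.

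The comparison that would expose the problem is Weight Only to historical. A Weight Only device behaves as an ordinary scale. In clinics that start on Weight Only and have not yet had balance mode, this ratio should therefore leave 1.0 only through drift, participation or chance. The counts are collected, but no interval or interpretation is planned for it.

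At stake is the reading of a plausible result: Balance+Weight to historical clearly above 1.0 with Balance+Weight to Weight Only near 1.0. That could be drift, or it could be carryover diluting the crossover contrast. The two planned ratios do not distinguish these.

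**Working it through.** **Inputs.** From section III.6: "an initial rate of an assessment of falls risk of 19% across 16 providers over 3 months leading to 360 screens"; 10 providers per group; nine months per period; "approximately 3552 patient encounters in each group, or 7105 patient encounters over 18 months"; target ratio 1.1. Two-sided 5% is implied by the 95% intervals. Drift sizes are assumptions, because the documents give none.

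**The plan's own figures.**
- 360 / 0.19 = 1894.7 encounters; / 16 providers / 3 months = 39.47 per provider-month.
- 39.47 × 10 × 9 = 3552.6 per group per period; doubled, 7105.3. Both are reproduced.
- Each condition is used by both groups, one period each, which gives 7105 encounters per condition. Twenty providers over a nine-month historical window also give 7105.
- At 7105 per condition, power for a ratio of 1.1 is 80.9% (binomial) or 71.7% (Poisson). At 3552 it is 51.7% or 43.3%. The plan's claim of sufficient power thus fits 7105 per condition.

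**Balance+Weight to historical with no device effect.** Expected historical codes: 7105 × 0.19 = 1350. For a true ratio r produced by drift alone:
- Poisson: SE(log) = √(1/1350 + 1/(1350r)). Binomial: subtract 2/7105 under the root.
- Chance that the interval excludes 1.0 ≈ Φ(ln r / SE − 1.96).

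| Rise since historical window | SE, Poisson / binomial | ln r / SE | Interval excludes 1.0 |
|---|---|---|---|
| 5% | 0.0380 / 0.0341 | 1.283 / 1.430 | 25% / 30% |
| 10% | 0.0376 / 0.0337 | 2.534 / 2.832 | 72% / 81% |

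An observed ratio of 1.10 would have a Poisson interval of about 1.02 to 1.18.

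**Steady drift.** The historical window matches the first study period (sections III.3 and III.4). Clinics using Balance+Weight first are therefore compared across 12 months, and those using it second across about 21. In 200,000 simulated trials with equal sequences and no device effect (binomial intervals):

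| Drift per year | Mean Balance+Weight / historical | Significant | Balance+Weight / Weight Only significant |
|---|---|---|---|
| 2% | 1.03 | 12% | 5% |
| 5% | 1.07 | 51% | 5% |
| 10% | 1.14 | 98% | 5% |

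With an assumed 60:40 volume split between sequences, the last column rises to about 5.5% at 5% a year and 7% at 10%.

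**Precision of the added ratios** (10 clinics per sequence, 3552 × 0.19 ≈ 675 codes per window):
- Weight Only to historical in Weight-Only-first clinics, period 1: SE = √(2/675) = 0.054; exp(1.96 × 0.054) gives ×/÷ 1.11. By the formula above with 3552 encounters, it detects a 5% rise 15% of the time (Poisson) or 17% (binomial), and a 10% rise 43% or 52%.
- Period-1 ratio of ratios: SE = √(4/675) = 0.077, ×/÷ 1.16. For a true device ratio of 1.1, SE = √(3/675 + 1/742.5) = 0.076 (Poisson) or 0.068 (binomial, subtracting 4/3552), so detection is Φ(0.0953/0.076 − 1.96) ≈ 24%, or 29%.

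All of this treats encounters as independent. Clinic-level variance would widen every interval that allows for it.

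**The case against.** The strongest reply is that the device question does not rest on the historical ratio. The objective in section I is balance plus weight in place of weight only, and the randomised crossover answers it. Participation is common to both conditions, and common drift cancels when the sequences carry similar volume. This stands. A reader might infer that the trial's device conclusion is exposed to drift; the documents do not support that.

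A reader might also infer that nothing in the analysis could reveal drift. That is too strong. The historical and Weight Only rates are both tabulated, and (Balance+Weight / historical) ÷ (Balance+Weight / Weight Only) gives the pooled Weight Only to historical point estimate. What is missing is an interval, a stated reading and a clean subset. The pooled quotient includes clinics that used Weight Only second, after nine months of balance data and the training in section III.4, so a lasting effect of that exposure would look like drift.

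A third temptation is to credit the device with whatever part of pooled Balance+Weight to historical exceeds the Weight-Only-first check. The time gaps differ. With no device effect, drift of 5% a year gives about 1.07 pooled, the mean of 1.05 and 1.05^(21/12) = 1.089, against 1.05 in the check. Drift of 10% gives 1.14 against 1.10. The leftover 2 to 4 percentage points would be credited to the device wrongly.

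Finally, the added check is weak. That also stands: a null result could reassure falsely.

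**Conclusion.** The point holds in a limited form. One of the two planned tests on the primary code cannot be interpreted alone, and the plan neither says so nor supplies the comparison needed to read it. At the plan's own volume, drift as large as the target effect (10%) would make that ratio significant in about 72 to 81% of trials with no device effect, and drift half that size in about 25 to 30%. These figures rest on 7105 encounters per condition, a 19% rate, encounter-level variance only and assumed drift. The randomised contrast survives, so this is a matter of ranking and reporting, worth correcting because the correction is nearly free.

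**What to change.** In section III.6, billing data:

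1. State that Balance+Weight to Weight Only carries the device conclusion, and that Balance+Weight to historical is supportive and is not on its own evidence of a device effect.
2. Report Weight Only to historical for CPT II 3288, with its 95% interval, in Weight-Only-first clinics in period 1 (same calendar months, never exposed to balance mode), as a drift check.
3. Report, as a supportive analysis, the period-1 baseline-adjusted ratio: (Balance+Weight-first clinics, period 1 / historical) divided by (Weight-Only-first clinics, period 1 / historical). It is free of carryover and removes common drift.
4. Do not read the excess of the pooled Balance+Weight to historical ratio over the check as a device effect.

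The cost is a few sentences; no new data, clinics or visits are needed. The downside is low precision (about ×/÷ 1.11 for the check and ×/÷ 1.16 for the ratio of ratios, wider with clinic-level variance). The text should therefore say that a null check does not rule out drift of 5 to 10% and that neither ratio replaces the crossover comparison.

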Recruitment of clinics to participate in study. Study personnel will recruit clinics to participate in an 18-month trial of the quantitative postural control assessment (Balance+Weight) device. Eligible clinics include any that self-report a substantial component of their patient population that may be at risk of falls, but that are not a referral site for patients previously identified as being at elevated falls risk. In clinics where multiple providers see patients, at least one provider must be willing to participate and commit to placing the novel device in their clinic, as well as to the other components of participation detailed below. Due to the number of ambulatory care clinics within a radius to allow same-day servicing of the devices and resource limitations to manufacture units, we will cap recruitment when we reach 20 clinics or 60 devices in service, whichever is reached first. Every participating clinic will have the opportunity to receive the device that delivers Balance+Weight either immediately or after a 9-month waiting period depending on randomization.

Randomization of clinics. A block randomization scheme by clinic type will be used to assign which clinics receive the Balance+Weight device in the first 9 months and which clinics receive the Balance+Weight device in the second 9 months. The block randomization scheme is proposed instead of simple randomization because of the expected variation between clinics in the types of patients they see. Blocks will be determined based on the estimated percent of patients seen who are over 65, diabetic, undergoing chemotherapy (all oncology clinics), or are using assistive devices during some of their care (e.g. orthopaedic trauma clinics). Clinics for whom 50% or more of their patients are in any of these categories will be included in one block, whereas clinics for whom less than 50% of their patients are in any of these categories will be included in the other block. While this scheme does not fully account for the confounder of multiple risk factors for falls or multiple co-morbidities in some clinics, equipoise between treatment arms is also achieved through the crossover design whereby every clinic serves as its own control as well.

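### The billing analysis (III.6) does not carry the clinic randomisation and crossover through: the variance and combination across clinics are unstated, no period term is fitted, and power rests on encounter counts alone

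*Combined protocol and SAP*

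**What the plan says.** III.2 (Sample) treats a site with several practitioners as one participant and lumps its primary outcomes together. III.4 (Randomization of clinics) states: "A block randomization scheme by clinic type will be used to assign which clinics receive the Balance+Weight device in the first 9 months". There are two blocks, defined by patient mix, and the section adds that "equipoise between treatment arms is also achieved through the crossover design whereby every clinic serves as its own control as well". Recruitment stops at 20 clinics or 60 devices, whichever comes first.

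I (Objective) and III.1 (Research Design), by contrast, say that providers are randomised. III.6 (Statistical analysis of clinical billing data) also works by provider: "Counts of each code listed above will be tabulated for each provider". It divides by that provider's encounters, forms IRRs of Balance+Weight to the other two conditions, and states that "the 95% confidence intervals of those incidence rate ratios will be calculated to see which are significantly different from 1.0". For the method it cites only reference 16.

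On size it says "we estimate that with 10 providers in each group over 9 months there could be approximately 3552 patient encounters in each group", or 7105 over 18 months, and "With this number of patient encounters, we would have sufficient power to detect an incidence rate ratio of 1.1". No power value is given. It adds that "that 10% increase could lead to approximately 47 additional high-risk individuals being identified".

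**The concern.** III.6 is the only analysis text for the second primary outcome. It leaves open how provider or clinic rates are combined, whether the contrast is paired within clinic, and which variance enters the interval. It has no term for period, block or clinic-by-period variation. Different analysts could follow it and reach different intervals and different conclusions.

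The crossover cancels stable differences between clinics. It does not cancel changes within a clinic between the two 9-month periods, such as staff turnover, a coding drive or a shift in patient mix. An interval that counts only encounters ignores that variation. A common period shift also enters the ratio if period is not fitted and the two sequences carry unequal event volumes. At stake are the false-positive rate of a primary test and a power claim that has no clinic-level basis.

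This point concerns Balance+Weight versus Weight Only. It does not address the historical comparison.

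**Working it through.** **Inputs from III.6:** 19% assessment rate, 360 screens, 16 providers, 3 months, IRR 1.1, 35% of assessed patients at high risk. **From III.2 and III.4:** 20 clinics. A 95% interval read against 1.0 implies a two-sided 5% test. **Assumed, not in the documents:** clinic-by-period SD, between-clinic CV of rates (0.5), clinic-size CV and period trend.

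**1. The plan's encounters.** 360 / 0.19 / 16 / 3 = 39.47 per provider-month. × 10 × 9 = 3552; × 10 × 18 = 7105. Both reproduce.

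**2. The plan's 47.** 7105 × 0.19 × 0.10 × 0.35 = 47.2; with 3552 it would be 23.6. So the plan counts 7105 encounters per condition.

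**3. Power if encounters are independent, 19% versus 20.9%.** For the Poisson interval, SE = √(1/(n × 0.19) + 1/(n × 0.209)) and power = Φ(ln 1.1 / SE − 1.96). At n = 7105, SE = 0.0376 and 0.0953 / 0.0376 − 1.96 = 0.57, giving 72%. The two-proportion formula gives 81%. At n = 3552 per condition the figures are 43% and 52%.

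**4. Null rejection if the interval is encounter-level.** Simulation: 20,000 trials per scenario, 20 equal clinics, 10 per sequence, 355 encounters per clinic-period (7105 / 20), 19% mean rate, no trend, no blocks. The last column is a t-test between sequences on each clinic's log(period-1 rate / period-2 rate).

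| Clinic-by-period SD (log rate) | Poisson | Binomial | Clinic t-test |
|---|---|---|---|
| 0 | 2.5% | 4.2% | 4.9% |
| 0.05 | 4.7% | 7.2% | 4.9% |
| 0.10 | 12.2% | 16.4% | 4.8% |
| 0.20 | 32.6% | 37.5% | 4.9% |

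**5. Break-even SD,** where the encounter-level variance equals the true one. Expected events per condition are 20 × 355 × 0.19 = 1349. With rate CV 0.5, the sum of squared event shares is 1.25 / 20 = 0.0625, and the true sampling variance carries the factor 1 − 0.19 × 1.25 = 0.7625, against 1 (Poisson) or 0.81 (binomial) in the interval.
- Poisson: √((1 − 0.7625) / (1349 × 0.0625)) = 0.053.
- Binomial: √((0.81 − 0.7625) / (1349 × 0.0625)) = 0.024.

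**6. Common period shift.** With no device effect, a 20% rise and a balanced 10/10 split of equal clinics, the pooled ratio is (10 + 12) / (12 + 10) = 1. With a 12/8 split it is (12 + 9.6) / (14.4 + 8) = 0.964. In simulation (10/10 split, clinic-size CV 0.6, SD 0, no blocks), null rejection for Poisson/binomial is about 3/5% for a 5% rise, 4/7% for 10% and 11/16% for 20%. With two blocks that explain half the log-rate variance, the 20% case falls to 9.8/14.1%.

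**7. Power of the clinic-level t-test, IRR 1.1.** With equal clinic rates, the variance of log IRR is [0.81/(355 × 0.19) + 0.791/(355 × 0.209) + 2 SD²] / 20. At SD 0 this is 0.00113, SE 0.0337, and power with 18 df is 76%. With between-clinic CV 0.5, simulated power at SD 0, 0.05, 0.10 and 0.20 is 65, 59, 44 and 23%. With 10 clinics it is 36, 31, 22 and 12%.

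**The case against.** The strongest reply is that the false-positive figures assume an interval the plan never states. A reader might infer that III.6 commits to treating encounters as independent, and hence that the primary test is anti-conservative. The documents do not support that. They give no interval method, and the content of reference 16 is not available, so it cannot be said to ignore clinics. The 47 fixes the encounter denominator and says nothing about the variance. The encounter-only power argument suggests an encounter-level interval but does not establish one.

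Second, the clinic is not wholly forgotten. III.2 lumps primary outcomes by site, the data-pull headings in III.3 and III.4 say clinic level, and 10 providers per group fits 20 single-participant clinics. Tabulating each provider under each condition leaves pairing possible. Pairing is unstated, not excluded, and part of the problem is wording.

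Third, the size of any harm depends on assumptions. Clustering alone does no damage here: at SD 0 without a trend the interval is nominal or conservative. A 5% trend gives at most about 5%; only a larger one matters.

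Fourth, part of the power loss comes from the replacement test. Equal weighting of clinics takes power from 76% to 65% at SD 0 when rates differ with CV 0.5.

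All four replies stand, and they limit the claim about size. None of them supplies the missing method, the period term or a clinic-level basis for power.

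**Conclusion.** The omission is clear from the text, and confidence in it is high. The design makes the clinic the participant, the randomised unit and its own control, and the analysis of a primary outcome does not say how that enters the estimate or its interval. The power claim reaches about 80% only with 7105 independent encounters per condition and binomial variance.

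The inflation is conditional. It needs an encounter-level interval together with clinic-by-period variation above about 0.05 (Poisson) or 0.02 (binomial) at 355 encounters per clinic-period, or a sizeable unfitted trend with unequal event volumes. The documents give no value for the variation or the trend, so they cannot show which side of break-even the trial lies on. Because this is the test of a primary outcome and the remedy is wording, it should be settled before the billing data are analysed.

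**What to change.** In III.6, name the clinic as the unit of analysis, and reconcile the provider wording in I, III.1 and III.6 with the clinic wording in III.2 and III.4. Pre-specify one period-adjusted, clinic-level primary analysis of Balance+Weight versus Weight Only for CPT II 3288, and state its interval method. Two options:

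- **Clinic-level t-test.** Sum counts and encounters to clinic and period. Take log(period-1 rate / period-2 rate) per clinic and compare the two sequences with df = clinics − 2, or − 3 with block as a covariate. A common period shift drops out of the difference between sequences. With the Balance+Weight-first sequence minus the other, IRR = exp(half the difference), with its 95% interval from the same test. Give a zero-count rule, for example adding 0.5 to both counts. State that this targets a clinic-average ratio, not a pooled one, and loses power when clinic volumes or rates differ.
- **Clinic-period count model.** Use a log(encounters) offset; device, period and block effects; clinic and clinic-by-period random effects; and a named small-sample df method. It was not simulated here, so check its error rate by simulation for the planned number of clinics before adopting it.

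Restate power for the chosen analysis, with a number, over a stated range of clinic-by-period SD, encounters per clinic and number of clinics.

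The cost is text only, because counts and encounters by provider and period are already planned and can be summed to clinic. The price is a probably wider interval and a less favourable power statement.

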Cover page

Title: Standing Balance as the Fifth Vital Sign in Clinical Setting

NCT04139642

Date: 10/17/2019

Does use of a quantitative balance measurement device influence clinical decision making?

PI: [name], PhD

I. Objective

This 18-month prospective, observational study involving real world data will determine if the use of a standing scale that delivers a quantitative measure of standing balance along with weight (balance + weight) in place of a scale that only delivers weight (weight only) influences clinical decision making by health care practitioners in the ambulatory outpatient setting. Providers will be randomized to receive the balance+weight scale or weight-only scale for 9 months, then to crossover and receive the other for 9 months. The primary outcome measures are (1) providers' self-reported perceptions of whether the balance measurement influences their clinical decision making and (2) the rate of performing falls risk assessments or referring to a specialist for evaluation and treatment based on aggregate billing data. The secondary outcome measure is qualitative interviews with practitioners regarding their perceptions on the utility and barriers to using the device.

II. Background and Rationale

Falls prevention efforts are poised to reduce the significant impact of this high-risk injury, but a critical component for success of a falls prevention program is measurement of risk for falls. While effective measurement is available, barriers prevent implementation due to the need for primary care providers to undertake assessment within the limited time available in the short patient visit.

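### The primary code CPT II 3288 is protected against a single comparator, but every other billing code, including an open set of referral codes, is also judged significant or not on an unadjusted 95% interval

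*Combined protocol and SAP*

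**What the plan says.** In III.6 Data Analysis (clinical billing data), counts of each code are divided by encounters to give a rate under three conditions: historical, Balance+Weight and Weight Only. "The incidence rate ratios of Balance+Weight to the other two conditions will then be calculated", and each ratio then gets a 95% interval "to see which are significantly different from 1.0". On handling several codes, the section says: "Each code is considered separately, because it is possible that multiple codes may be used in a single encounter". The same sentence adds that "the primary variable of interest is CPT II 3288: Assessment of falls risk".

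The code list in III.4 (data pull) marks CPT II 3288 as primary, adds 0518, 1101 and 1100, and ends with "Other referral codes as appropriate". It describes the list as an initial plan and allows yearly revision as CPT codes change.

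The billing primary outcome is worded more broadly elsewhere. In I. Objective it is "the rate of performing falls risk assessments or referring to a specialist for evaluation and treatment based on aggregate billing data". In III.1 Research Design it covers diagnosis, procedure and referral patterns.

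No section gives a multiplicity adjustment or a testing order, labels the other codes secondary or exploratory, or says which of the two comparators is primary.

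**The concern.** Naming one primary code normally contains the error, because the conclusion rests on that code and the rest is supportive. Three features of this plan weaken that.

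- **The significance criterion is not confined to the primary code.** It covers the ratios of every code, and nothing says what a significant result on another code would mean.
- **The outcome wording is wider than the primary code.** Under the Objective and Research Design, a significant referral code would count as a change in the billing primary outcome even if CPT II 3288 showed nothing.
- **Referral is the part with no fixed code list.** Nothing requires the referral codes to be chosen before the first data pull.

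At stake is the study's own question, whether the device changes clinical decisions. One non-primary code moving by chance could be presented as evidence that it does.

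**Working it through.** **The plan's own figures.** The plan states no error rate across codes. It does give the encounter volume behind its power statement, and that reproduces:

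- (360 / 0.19) / 16 / 3 = 39.47 encounters per provider-month
- 39.47 × 10 providers × 9 months = 3552.6, and twice that is 7105.3
- 7105.3 × 0.19 × 0.10 × 0.35 = 47.25 additional high-risk individuals

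These match the stated 3552, 7105 and 47. All of them concern falls risk assessment, so the planning calculation rests on CPT II 3288 alone.

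**Inputs from the documents.** Four named codes, of which three are non-primary; two comparators per code; 95% intervals, which imply a two-sided 5% error per ratio.

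**Assumptions.** No true effect on the codes being counted; intervals correctly calibrated; correlation between codes from 0 to 0.8 (the documents give none); for the six-code rows, two referral codes (the documents give no number).

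**Independent codes, one comparator.** The chance of at least one false significant ratio among k codes is 1 − 0.95^k.

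- Three non-primary codes: 1 − 0.95³ = 0.143
- All four named codes: 1 − 0.95⁴ = 0.185

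**Correlated codes and two comparators.** Both ratios for a code share the Balance+Weight rate, so they are correlated at about 0.5 and cannot be treated as independent. I simulated normal log rates for the three conditions with equal variances and a common between-code correlation, and counted draws in which any |z| exceeded 1.96.

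| Codes counted | Comparators | Correlation 0 | Correlation 0.8 |
|---|---|---|---|
| 3288 only | 1 | 5.0% | 5.0% |
| 3288 only | 2 | 9.0% | 9.1% |
| Four named | 1 | 18.5% | 11.5% |
| Four named | 2 | 31.6% | 19.9% |
| Six (two referral codes assumed) | 1 | 26.5% | 13.8% |
| Six (two referral codes assumed) | 2 | 43.5% | 23.9% |

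For the three named non-primary codes against Weight Only, the figure falls from 14.3% to 11.8% at an assumed correlation of 0.6. It applies whether or not the device truly changes 3288, because it counts only the other codes.

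**Cost of a blanket correction.** Take 7105 encounters per condition, a rise from 19% to 20.9%, a two-sided test of two proportions, and no allowance for clustering by clinic. Power for 3288 is then 80.9%. Bonferroni over four ratios (0.0125 each) lowers it to 63.2%, and over eight (0.00625 each) to 54.0%. Testing 3288 first at the full 5% avoids that loss.

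The kiosk outcome is not counted, because it is an estimated proportion and a kappa with no stated null value.

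**The case against.** The strongest reply is that the sponsor has already chosen. CPT II 3288 is marked primary in both the code list and the analysis section, and the stated hypothesis, the power statement and the yield of 47 all belong to it. Leaving non-primary measures unadjusted is common in a study that calls itself observational. This largely stands. A reader might infer that the study's main conclusion carries an error rate well above 5%, or that the plan declares success if any code moves. The documents support neither: no any-code success rule is written, and 3288 against one comparator stays at 5%.

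Other replies stand in part:

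- **Wording.** The clause asking which ratios differ may refer to the two comparators rather than to a scan of codes. But ratios are formed for each code separately, so the criterion reaches every code on either reading.
- **Direction.** The hypothesis is that assessment becomes more likely, and the two-sided figures also count decreases. A false increase on any of four independent codes has probability 1 − 0.975⁴ = 9.6%, against a nominal 2.5%. The absolute figure is smaller, but the relative inflation is similar.
- **Correlation.** These codes arise from one workflow and may be recorded in the same encounter, so independence is the least plausible case. That is why the range down to 0.8 is given; at 0.8, four codes against one comparator still give 11.5%.
- **Safeguards.** Yearly revision follows external CPT updates, and III.5 Internal Validity promises blinded analysts. Both limit choosing codes by result, but neither fixes how many are tested, and the referral item remains open.

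**Conclusion.** The point holds for the non-primary and referral codes, and for any conclusion of the form that some code changed. It does not hold for CPT II 3288 against a single comparator. For the three named non-primary codes against Weight Only, the chance of at least one false significant ratio is 14.3% if independent and about 12% at correlation 0.6. For all four codes it is 18.5% to 11.5% with one comparator and about 32% to 20% with both, and it rises with each referral code added. Because the primary comparator is not named, 3288 itself carries about 9% if a difference from either comparator would count.

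These sizes rest on assumed correlations and on calibrated intervals. The direction does not depend on the exact correlation: short of perfect correlation, testing several codes unadjusted gives more than 5%. What makes this more than a labelling preference is the conflict between a single-code primary in III.4 and III.6 and a primary outcome that includes referral in I and III.1.

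**What to change.** - **III.6:** replace the significance criterion for all ratios with one confirmatory claim: CPT II 3288, Balance+Weight versus Weight Only. That is the randomised comparison; the historical one is not. Report all other codes, and all historical ratios, as ratios with 95% intervals, labelled descriptive and without a significance statement.
- **I and III.1:** align the wording of the billing primary outcome with that single comparison, so that referral is no longer primary in one place and unranked in another.
- **Only if claims on other codes, including referral, are wanted:** fix the list in III.4 before the first data pull, allow only changes forced by CPT updates, and apply Holm across that list once 3288 is significant.

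The cost is one or two sentences in the analysis section plus matching edits in the other two. CPT II 3288 keeps its full 5% and loses no power. The downside is that secondary codes can no longer be called significant on an unadjusted 95% interval.
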